5.5. Schedule of Visits and Procedures

5.5.1. Pre-treatment phase

Day -21 to Day 0

Before performing any procedures or assessments, the investigator's staff will explain the nature of the study and the potential risks associated with the study to all subject candidates and their respective partners where applicable, and obtain written informed consent from both if required. Once the IRB/IEC-approved ICF has been signed, the following procedures and evaluations will be performed:

- Determination of eligibility (inclusion/exclusion criteria, Section 3):
- Record demographic data
- Evaluate ECOG PS score (must be 0, 1 or 2 for subject to be eligible) (Appendix 2) and cardiovascular status per NYHA criteria (Appendix 4)
- Record medical and surgical history
- Record all prior and concomitant medication use (prescription and nonprescription medications as well as transfusions) beginning 30 days before the start of study treatment (except record all previous breast cancer treatments)
- Perform physical examination

- Obtain vital signs (BP, HR, respiratory rate, and body temperature), weight, and height.
- Perform tumor assessments to identify target and nontarget lesions. Computed tomography or MRIs are to be obtained between Day -21 and Day 1. Confirm the presence of at least one measurable lesion ≥ 10 mm in the longest diameter for a non-lymph node or ≥ 15 mm in the short-axis diameter for a lymph node
- Obtain bone scan within 6 weeks before start of study treatment.
- Perform a 12-lead ECG
- Collect serum or urine sample for β -hCG pregnancy testing from all premenopausal and any postmenopausal women who have been amenorrheic for < 12 months
- Collect blood samples for clinical chemistry and hematology analyses (see Table 4) for a list of tests to be performed).
- Collect blood samples for whole blood for germline DNA SNP analysis
- Record any AEs (from the time of the first dose of study treatment)
- Schedule Cycle 1 Day 1 Visit: Screening assessments may serve as baseline assessments if they are performed within 3 days before the first dose of study treatment.

5.5.2. Assessments in the Treatment Phase

Reasonable effort should be made to conduct study visits on the day scheduled (± 3 days). The Study Calendar is provided in Table 3.

Day 1 of Treatment

- Record ECOG PS score (for Cycle 1: record if not done at Baseline visit)
- Record weight (for Cycle 1: record if not done at Baseline visit)
- Record vital signs (BP, HR, respiratory rate, body temperature) before administration of eribulin mesylate.
- Perform one post baseline 12-lead ECG on Day 1 of Cycle 2 before administration of study treatment
- Perform physical exam
- Collect blood samples for clinical chemistry and hematology analyses within 3 days before the scheduled visit (see Table 4 for a list of tests to be performed). Laboratory assessments are not required on Day 1 of Cycle 1 if already performed at Baseline (within 3 days before study administration)
- Review all laboratory results before administering study treatment

- Record all concomitant medication use
- Cycle 1 D1, cycle 2 D1, cycle 3 D1, and every other cycle (i.e., cycles 5, 7, 9 until treatment discontinuation) - Administer QOL surveys (FACT-B, FACT-Ntx, and PRO-CTCAE) and complete physicians reported CTCAE as detailed below:
 - Administer the QOL surveys (FACT-B, FACT-Ntx, and PRO-CTCAE). Assessments may be performed within 3 days before the scheduled
 - Record selected provider-reported CTCAE (detailed in Table 3). Adverse events should be graded as the worst grade in the last 7 days, which is different from standard CTCAE grading which typically spans the duration of time since the prior clinical assessment or treatment. Attempts should be made to have provider-reported CTCAE and QOL surveys performed on the same day.
- Administer study treatment:
- Eribulin mesylate 1.4 mg/m² as an i.v. infusion over approximately 2 to 5 minutes
- Record any AEs or SAEs

Day 8 of Treatment

- Record weight
- Record vital signs (BP, HR, respiratory rate, body temperature) before the administration of eribulin mesylate
- Collect blood samples for hematology and chemistry analyses within 24 hours before the scheduled visit (see Table 4 for the tests to be performed).
- Review all laboratory results before administering study treatment.
- Administer study treatment:
- Eribulin mesylate 1.4 mg/m² as an i.v. infusion over approximately 2 to 5 minutes

Tumor Assessments Interval

Tumor assessments will be performed every 9 weeks, up to 1 week before the administration of the first dose of study treatment in the next treatment cycle as indicated in the Study Calendar (Table 3):

- Confirm Complete Response (CR) or Partial Response (PR) a minimum of 4 weeks after initial response assessment. Bone scan and brain CT/MRI at treating physician discretion. Scans can also occur as clinically indicated for new symptoms or to confirm disease response. Radiological scans that were negative at baseline do not have to be repeated unless clinically indicated.

End-of-Treatment Visit in the Treatment Phase

Subjects will continue to receive study treatment until PD or another withdrawal criterion is met, as described in Section 5.9. If a subject develops PD study treatment must be discontinued and end-of-treatment assessments be performed within 21 days of discontinuation of study treatment. If study treatment is discontinued without the subject having PD, the subject will undergo end-of-treatment assessments and enter the posttreatment Follow-up Period for tumor response assessment.

5.5.3. End-of-Treatment Procedures

All subjects will be asked to return to the site for a final, End-of-Treatment visit, if possible. The End-of-Treatment visit must be performed within 21 days of final administration of study treatment. End-of-treatment assessments will not have to be repeated if the same assessments were performed within 7 days of this visit.

End-of-Treatment Visit

- Perform tumor assessments as indicated in the Study Calendar (Table 3). If study treatment is discontinued due to PD, then tumor assessments are not required for that subject.
- Evaluate ECOG PS
- Perform physical exam
- Record vital signs (BP, HR, respiratory rate, body temperature) and weight
- Collect blood samples for hematology and serum chemistry analyses (see Table 4 for a list of tests to be performed)
- Record all concomitant medication use. Concomitant medications should be collected for 30 days after the last dose of study treatment.
- End of treatment visit - Administer QOL surveys (FACT-B, FACT-Ntx, and PRO-CTCAE) and complete physicians reported CTCAE as detailed below:
 - Administer the QOL surveys (FACT-B, FACT-Ntx, and PRO-CTCAE) survey. Assessments may be performed within 3 days before the scheduled clinic visit.
 - Record selected physicians reported CTCAE (detailed in table 2). Adverse events should be graded as the worst grade in the last 7 days, which is different from standard CTCAE grading which typically spans the duration of time since the prior clinical assessment or

treatment. Physicians reported CTCAE and QOL surveys should be performed in the same day.

- Record any AEs or SAEs

All AEs, regardless of relationship to study treatment or procedure or grade, will be collected from the time the subject signs the study ICF until 30 days after discontinuation of study treatment. Any AEs must be followed until resolution or for 30 days after the subject's last study visit, whichever comes first. However, treatment-emergent peripheral neuropathy and alopecia will be followed until resolution or another anticancer agent is started, whichever occurs first. Serious AEs will be collected for 30 days posttreatment and followed until resolution or, if resolution is unlikely, until the event or sequelae stabilize or returns to baseline levels.

5.5.4. Follow-up Period Procedures

Subjects who do **not** have PD upon discontinuation of study treatment are to have tumor assessments during the post treatment Follow-up Period (using the same methodology and acquisition techniques as were used for previous assessments) every 9 weeks from the date of the last tumor assessment until PD is documented (see the Study Calendar in Table 3. During the Follow-up Period, subjects who have treatment-emergent peripheral neuropathy during the study will be followed until resolution of the neuropathy, or until another anticancer therapy is started, whichever occurs first.

5.6. General Concomitant Medication and Supportive Care Guidelines

All diagnostic, therapeutic, or surgical procedures relating to malignancy should be recorded in the electronic case report form (eCRF), including the date, indication, description of the procedure(s), and any clinical findings. All previous treatments for breast cancer should be included.

All prior treatment or medication administered during the 30 days preceding the first dose of study treatment and any concomitant therapy administered to the subject throughout the study until 30 days after the final dose of study treatment must be recorded on the Prior and Concomitant Therapy page of the eCRF. The generic name of the drug (or trade name for combination drugs) must be specified along with the duration of treatment and indication for use. If concomitant medication/therapy is administered for an adverse event (AE), investigators will record that AE on the AE page of the eCRF.

Any medication that is considered necessary for the subject's welfare and that is not expected to interfere with the evaluation of study treatment may be given at the discretion of the investigator. Ancillary treatments will be given as medically indicated.

Any changes in documented, permitted concomitant treatment already being taken at the start of the clinical study must be recorded on the eCRF, noting the type of medication, duration of use, and indication.

5.6.1. Premedication

Premedications (anti-emetics) may be administered before eribulin mesylate administration, but are not required. Premedication with steroids or antihistamines to prevent hypersensitivity reactions is not required.

5.6.2. Permitted concomitant Therapies and Medications

The following agents are permitted, except as noted:

- Antiemetics
- Antidiarrheal therapy
- Antiallergic measures such as corticosteroids and antihistamines
- Granulocyte colony-stimulating factor (G-CSF), granulocyte-macrophage colony-stimulating factor (GM-CSF), and erythropoietin in accordance with American Society of Clinical Oncology guidelines and local standard practice.
- Bisphosphonates: Subjects being treated with bisphosphonates when they enter the study may continue the medication as long as the dose is stable. Subjects may also initiate bisphosphonate therapy while on protocol therapy if it is thought to be medically necessary.
- Palliative radiotherapy may be given for bone pain or for other reasons (i.e., bronchial obstruction, ulcerating skin lesions). The irradiated area should be limited and should not involve more than 10% of the bone marrow. The irradiated area cannot be used for tumor response assessment.
- During palliative radiotherapy, treatment with study treatment should be held. Treatment with study treatment may be resumed within 14 days after completion of radiotherapy if the subject has recovered from any radiation-associated toxicity.
- Ovarian suppression with goserelin or leuprolide are allowed on study.

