1. OBJECTIVES

1.1. Study Design

This is a non-randomized, open label study of eribulin monotherapy in the first or second line setting for metastatic HER2-negative breast cancer. Patients will be enrolled in 2 parallel cohorts. Cohort 1: Hormone receptor (HR)-positive /HER2-negative (HR+/HER2-). Cohort 2: HR-negative/HER2-negative (triple negative breast cancer [TNBC]). A total of 45 patients will be included in the HR-positive cohort and 45 in the TNBC cohort.

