3. PARTICIPANT SELECTION

3.1. Eligibility Criteria

Subjects who meet all of the following criteria may be included in this study:

- Female or male age 18 years or older at the time of informed consent
- Have histologically or cytologically proven invasive breast cancer, locally recurrent or metastatic, with at least one measurable lesion according to RECIST v 1.1 (Appendix 1). Measurable disease is defined as: At least one lesion of ≥ 10 mm in the longest diameter for a non-lymph node or ≥ 15 mm in the short-axis diameter for a lymph node which is serially measurable according to RECIST criteria, using CT or MRI
- Patients may have hormone receptor positive or hormone receptor negative HER2-negative disease. Hormone receptor positivity (ER and/or PR) is defined by at least 1% of positive tumor cells in the sample by immunohistochemistry (IHC). “Triple negative” is defined by the lack of estrogen and progesterone receptor and by HER2-negative status. HER2-negative disease can be determined by FISH or IHC. Negativity by IHC is defined as scores of 0 or 1+. Borderline IHC results (i.e., 2+) should undergo FISH testing; subjects with an HER2 FISH ratio ≤ 2.0 are eligible.
- Prior therapies
 - Up to one prior line of chemotherapy for advanced disease is allowed. If received, prior chemotherapy must be discontinued at least 14 days prior to initiation of protocol therapy.
 - Prior bevacizumab in the neo/adjuvant or metastatic setting is acceptable.
 - No limit on prior lines of endocrine therapy or biologic therapy. Endocrine therapy and biologic therapy must be discontinued at least 7 days prior to initiation of protocol therapy.
 - Patients must have completed any prior radiotherapy at least 2 weeks prior to initiation of protocol therapy.
 - Patients must have recovered from any reversible effects of prior therapies to no more than Grade 1 toxicity, with the exception of alopecia.
- ECOG PS score of 0, 1 or 2 (see Appendix 2)
- Participants must have normal organ and marrow function as defined below

- Creatinine ≤ 1.5 mg/dL or calculated creatinine clearance ≥ 40 mL/min per the Cockcroft and Gault formula (Appendix 3)
- Absolute neutrophil count $\geq 1.5 \times 10^9/L$
- Hemoglobin ≥ 9 g/dL
- Platelet count $\geq 100 \times 10^9/L$
- Bilirubin ≤ 1.5 times (x) the institutional ULN
- ALT and AST ≤ 3 x ULN, or ≤ 5 x institutional ULN in subjects with liver metastasis.
- ECG QTC interval < 470 ms

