5.6.3. Prohibited Concomitant Therapies and Drugs

The use of investigational or other antitumor therapies, other than eribulin mesylate is prohibited during this study. If subjects receive additional antitumor therapies such as chemotherapy, hormone therapy (tamoxifen, aromatase inhibitors, fulvestrant), radiation therapy other than required for palliation, gene therapy, biologics, or immunotherapy, irrespective of the reason for which they are being given, this will be judged to represent evidence of progressive disease (PD) and study treatment will be discontinued. These subjects will complete all end-of-treatment assessments.

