14. STATISTICAL METHODS

14.1. Statistical and Analytical Plans

Statistical programming and analyses will be performed using SAS and other validated statistical software as required.

The primary analyses of efficacy endpoints that are related to tumor assessment will be performed using investigator-assessed data.

The full analysis dataset will include all subjects who receive at least one dose of study treatment. Objective response will be assessed according to RECIST 1.1. All patients who receive at least one dose of therapy will be included in the calculation of objective response rate. Patients who, in retrospect, do not have measurable disease, and patients with no follow up evaluation of response, will be considered non-responders for the purpose of analysis of the primary endpoint. Confirmation of response is required to assign a status of best overall response of CR or PR.

Patients who have developed metastatic disease within 12 months of last dose of (neo) adjuvant chemotherapy who enroll on protocol will be considered in the analysis as a second-line patient, even if no prior chemotherapy was received in the metastatic setting.

Demographic and Other Baseline Characteristics

Demographic and other baseline characteristics will be listed, and summarized for the full analysis dataset. For continuous demographic/baseline variables such as age, weight, and vital signs, results will be summarized and presented as number (N), mean, median, and range. For categorical variables such as race/ethnicity, the number and percentage of subjects will be used.

Subject Disposition

The number and percentage of subjects, who complete or prematurely withdraw from the study, as well as the reason for discontinuation, will be summarized.

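### Ovarian suppression may start on study at any time, and no analysis separates a response that follows it from single-agent eribulin activity in the HR-positive cohort

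*Combined protocol and SAP*

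**What the plan says.** Three sections bear on ovarian suppression, but only one names it.

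- **Section 3.1 (prior therapies):** "Endocrine therapy and biologic therapy must be discontinued at least 7 days prior to initiation of protocol therapy". No exception is given.
- **Section 5.6.2 (permitted therapies):** "Ovarian suppression with goserelin or leuprolide are allowed on study". There is no start date, prior-use condition or cohort restriction. Other items in the same list are qualified. For bisphosphonates, "Subjects being treated with bisphosphonates when they enter the study may continue the medication as long as the dose is stable", and starting them on study is addressed separately. An area given palliative radiotherapy is barred from response assessment.
- **Section 5.6.3 (prohibited therapies):** "The use of investigational or other antitumor therapies, other than eribulin mesylate is prohibited during this study". The therapies listed include "hormone therapy (tamoxifen, aromatase inhibitors, fulvestrant"). If one is given, for whatever reason, "this will be judged to represent evidence of progressive disease (PD) and study treatment will be discontinued". Goserelin and leuprolide are not named.

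On the analysis side, Section 1.2 defines the primary objective as the activity of single-agent eribulin. Section 14.1 says "All patients who receive at least one dose of therapy will be included in the calculation of objective response rate". Sections 10.3 and 14 contain no rule, flag or sensitivity analysis for ovarian suppression. Section 14.2 sets the HR-positive cohort of 45 against a fixed historical rate of 30%.

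**The concern.** The primary endpoint is meant to describe eribulin alone. An HR-positive patient who begins goserelin or leuprolide after the baseline scan has a second treatment running while target lesions are compared with that scan. Whether such a drug can shrink the tumor is not stated in the documents. However, the cohort is defined by hormone-receptor expression, and Section 5.6.3 treats hormone therapy as antitumor therapy.

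How the patient is scored depends on which section is applied. If 5.6.2 governs, a confirmed response counts in full. If the drug is hormone therapy under 5.6.3, the same patient is judged to have progressed. With one arm and a fixed comparator, the design cannot remove a second agent's contribution, and the analysis plan does not show how many patients are affected.

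**Working it through.** **1. Reproduce the plan's figures (Section 14.2).** Inputs: n = 45, threshold 20 responses, null 30%, alternative 53%, two-sided 0.1 exact binomial test, stated power 90%.

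- Exact 90% lower confidence bound: 0.297 at 19/45 and 0.317 at 20/45. Table 5 gives .297 and .317, so 20 is the correct threshold for exceeding 30%.
- P(X ≥ 20 | n = 45, p = 0.30) = 0.028. The nominal upper tail is 0.1/2 = 0.05.
- P(X ≥ 20 | n = 45, p = 0.53) = 0.903, which agrees with the stated 90%.

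The sample size and power are sound. The question is attribution only.

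**2. Trace a newly started patient through the text.**

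| Reading | Is the drug allowed? | Score of a confirmed response |
|---|---|---|
| 5.6.2 is an exemption from 5.6.3 | Yes, from any date | Full eribulin response |
| Ovarian suppression is hormone therapy under 5.6.3 | No | Progression from the time it is given; treatment stops |

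Under the first reading, whether the 3.1 washout applies to ovarian suppression already in use is still open, because 3.1 makes no exception.

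**3. Illustrate the size under the first reading.** Two inputs are not in the documents and are assumed:

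- f = share of Cohort 1 starting ovarian suppression on study, 5% to 30%
- q = chance of a confirmed response from it in a patient who would not respond to eribulin, 10% to 30%

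With the true eribulin rate at the 30% null, the observable rate is p = 0.30 + f × q × 0.70. The expected number of extra responders is 45 × f × q × 0.70. Example: f = 0.10 and q = 0.20 give p = 0.30 + 0.014 = 0.314 and 0.63 extra responders.

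| f | q | p | Extra responders | P(X ≥ 20 of 45) |
|---|---|---|---|---|
| – | – | 0.300 | 0 | 0.028 |
| 5% | 10% | 0.3035 | 0.16 | 0.032 |
| 5% | 30% | 0.3105 | 0.47 | 0.040 |
| 10% | 20% | 0.314 | 0.63 | 0.045 |
| 10% | 30% | 0.321 | 0.94 | 0.056 |
| 20% | 20% | 0.328 | 1.26 | 0.068 |
| 20% | 30% | 0.342 | 1.89 | 0.100 |
| 30% | 30% | 0.363 | 2.83 | 0.163 |

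The probability passes 0.05 at just under one expected extra responder in the cohort. Below that it stays inside the tail that the design already permits.

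**The case against.** The strongest reply is that there is no contradiction. Section 5.6.2 gives specific permission for two named drugs, the adjacent general ban omits them from its list of hormone therapies, and the washout in 3.1 concerns treatment before entry. That is the most natural reading, so a reader who inferred that the three sections flatly conflict would be going too far. What stands against the reply is that the exemption settles permission but not scoring, and that 3.1 and 5.6.3 never state it.

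A reader might also infer that tumor shrinkage from ovarian suppression is being credited to eribulin and that Cohort 1 ORR is therefore inflated. The documents do not support that as fact. They do not classify goserelin or leuprolide as antitumor therapy, and they give no menopausal mix, uptake or response rate. Section 14.2 does not say whether the historical studies behind the 30% allowed ovarian suppression; if they did, part of any contribution is already in the benchmark. Nothing here quantifies an effect on progression-free survival or response duration.

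Nor does the narrow gap between 19 and 20 responses mean that one misattributed response decides the trial. It matters only if the count would otherwise be exactly 19, which at a true 30% has probability 0.0549 − 0.0283 = 0.027. Section 14.2 also describes the objective as estimation and ties no decision to 20/45.

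These points limit the size of the concern. They do not close the gap, because the plan as written would not reveal whether it mattered.

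**Conclusion.** The concern holds as an attribution gap in the Cohort 1 primary endpoint, not as an error in the design figures or a demonstrated bias. When 5.6.2 is read as an exemption, every confirmed response after newly started ovarian suppression is reported as single-agent eribulin activity, and nothing in Section 14 separates it.

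Over the assumed ranges (f 5-30%, q 10-30%, true eribulin ORR 30%), P(X ≥ 20 of 45) lies between 0.032 and 0.163, compared with 0.028 under the plan and a permitted 0.05. The range is driven entirely by the assumptions, and the effect is negligible if few patients start the drug. That the drugs can produce a response in HR-positive disease is itself an assumption.

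**What to change.** 1. **Reconcile Sections 3.1, 5.6.2 and 5.6.3** on whether ovarian suppression counts as endocrine or hormone therapy and when it may be in use. The clinical rule is for the sponsor to decide.
2. **Keep the primary ORR unchanged.** In Section 14.1, add a supplementary Cohort 1 ORR in which patients who began goserelin or leuprolide after the baseline scan and before response count as non-responders. Report their number beside it. Label it a conservative lower bound, because it may also discard genuine eribulin responses.
3. **Confirm that the eCRF records the start date.** For concomitant drugs, Section 5.6 specifies duration and indication and does not mention a start date; without one the supplementary analysis cannot be run.

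The cost is a wording change, possibly one eCRF field, one extra table line, and a supplementary ORR that may be lower than the primary one. If few patients are affected, the added line will show that.
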